1.1 Identification of the clinical investigation plan

a) Title

Researching the effectiveness of *alivis*, a digital health application for Borderline Personality Disorder: a randomized controlled trial (REVALDI-BPD)

b) Reference number

This trial will be registered in an international trial registry before the start of recruitment.

c) Version / Date

version 5 / 28.03.2025

d) Summary of the revision history

version 2 (14.08.2023): changes in endpoints, control condition, in- and exclusion criteria, and associated procedures. Video instead of telephone interviews. Moreover, the description of the program was updated to reflect more clearly which therapeutic strategies are used. All changes are marked in yellow.

version 3 (18.01.2024): change of PI. Telephone instead of video interviews. Details on monitoring have been added in section 6.5. All changes are marked in green.

version 4 (18.07.2024): removal of BPD-CL als secondary endpoint; further information on *alivis* and the development process; updated formulation of primary and secondary hypotheses; changes control group from TAU + information material to TAU only; further information on the emergency plan for suicidal crises; change of responder criteria; updated exclusion criteria; added subgroup analyses; added information on the estimand strategy; updated information on funding. All changes are marked in pink.

version 5 (28.03.2025): updated exclusion criterion from “Plans to change treatment in the upcoming 6 months after inclusion” to “Plans to change treatment in the upcoming 3 months after inclusion”. All changes are marked in orange.

e) Version/issue number and reference number

version 5

f) Abbreviations

ACT	Acceptance and Commitment Therapy
ANCOVA	Analysis of Covariance
AQoL-8D	Assessment of Quality of Life - 8 Dimensions
BPD	Borderline Personality Disorder
BSL-23	Borderline Symptoms List-23
ClinROM	Clinician-reported outcome measure
DBT	Dialectical Behavioral Therapy
DiGA	Digital health application
DSM-V	Diagnostic and Statistical Manual of Mental Disorders
GAD-7	Generalized Anxiety Disorder Assessment
GDPR	General Data Protection Regulation
ICMJE	International Committee of Medical Journal Editors
ITT	intention to treat
MCID	minimal clinically important difference
NPS	Net Promoter Score
PHQ-9	Patient Health Questionnaire
PP	per protocol
PROM	Patient-reported outcome measure
PRRC	Person Responsible for Regulatory Compliance
QMS	Quality Management System
RCT	randomized controlled trial
SCID-5-PD	Structured Clinical Interview for DSM-5
ST	Schema Therapy
T0	Baseline
T1	primary timepoint for analysis of effectiveness; 3 months post allocation
T2	6 months post allocation
T3	12 months post allocation
TAU	Treatment as usual
WAI	Working Alliance Inventory
WSAS	Work and Social Assessment Scale

~~ZAN-BPD~~ ————— ~~Zanarini Rating Scale for Borderline Personality Disorder~~

1.4 Overall synopsis of the clinical investigation

This randomized controlled trial (RCT) with 470 patients diagnosed with Borderline Personality Disorder (BPD) aims to investigate the effectiveness of the unguided digital therapeutic *alivis* for patients with BPD as defined in DSM-5. Inclusion criteria are: male, female or non-binary, age 18-65 years, diagnosis of BPD (confirmed by SCID-5-PD), borderline severity score (cut-off) of ≥ 1.07 on the Borderline Symptoms List 23 (BSL-23), stable treatment (e.g., psychotherapy, medication, no treatment,...) for at least 30 days at the time of inclusion, consent to emergency plan for suicidal crises, consent to participation, and sufficient German language skills. Exclusion criteria are: Plans to change in treatment (e.g., psychotherapy, medication,...) in the upcoming 3 months after inclusion, comorbid diagnosis of substance use disorder or lifetime diagnosis of psychotic disorder, physical condition that can cause severe psychiatric symptoms, acute decompensation of mental health, BMI <15 , and prior use of the digital intervention *priovi*.

Patients will be randomized and allocated to either an intervention group, in which they will receive access to *alivis* in addition to treatment as usual (TAU; n=235), or to a control group, in which they will receive access to TAU and publicly available information material on BPD (n=235).

The primary endpoint will be BPD symptoms with three months post-allocation (T1) being the primary timepoint for assessment of effectiveness. Six (T2) and twelve (T3) months post-allocation will be used as follow-up assessment of endpoints. Secondary endpoints will be depressive symptoms, anxiety symptoms, costs caused due to the patient's BPD, social functioning, mental-health-related quality of life, ~~specific BPD symptoms (on the basis of all nine BPD criteria according to DSM-5)~~, and patient activation. For a visualization of the trial design, see figure 1.

1.5 Introduction

Borderline Personality Disorder (BPD) is a common, debilitating and costly mental disorder which is characterized by an instability in interpersonal relations, behavior, and emotions (1–4). Individuals with BPD experience symptoms ranging from frantic efforts to avoid abandonment and chaotic relationships, to a distorted self-image, feelings of emptiness, emotional dysregulation, dissociation, and intense anger, impulsive behaviors, self-harm, and suicidal ideation (3).

Several effective psychotherapeutic approaches for BPD exist (5,6), including dialectical behavior therapy (DBT), schema therapy (ST), and mentalization-based treatment. However, fewer than one in four BPD patients have access to psychotherapy (7). Digital health applications (DiGAs) can provide evidence-based psychotherapies that may help to reduce this treatment gap (8). DiGAs are also suitable for patients who prefer to overcome their mental health problems on their own or for those who live in areas with low access to psychiatric-psychotherapeutic care. This evidently applies to a considerable proportion of those who have a serious mental illness but do not seek treatment (9,10).

To date, a couple of digital health applications for BPD exist, which focus on tools from ST or from DBT (11,12). *alivis* is based primarily on DBT, which is the best-evaluated behavioral treatment method for BPD (5,13). DBT is a modular treatment program, and *alivis* makes use of several of these modules: for example, skills in emotion regulation, distress tolerance, antidissociative techniques, interpersonal effectiveness, and mindfulness are taught. These DBT modules are expanded in *alivis* to include modules on basic needs from ST (14,15), which has a good evidence base in BPD (13,16,17), on values work and defusion techniques from Acceptance and Commitment Therapy (ACT; 18–20) as well as on fostering self-compassion from Mindfulness Self-Compassion Therapy (MSC; 21) adapted to the needs of patients with BPD. Similar techniques have been integrated into more recent DBT protocols (22,23). The composition of the techniques used in *alivis* is thus based on the latest findings in psychotherapy research as well as on the extensive clinical expertise of the development team. Providing such a wide range of strategies enhances the chances that the patient will be able to make use of what they are offered and eventually profit from the intervention. *alivis* was developed by clinicians and researchers with long-standing expertise in the field of BPD which they have incorporated into the development of *alivis*, and with the involvement of patients suffering from BPD.

The aim of the present RCT is to examine the effectiveness of *alivis*, a self-guided digital intervention for BPD, to decrease symptom severity in BPD patients.

2. Identification and description of the investigational device

a) Summary description

Participants allocated to the intervention group will be provided with access to the program *alivis*. *alivis* is a CE-labeled, interactive online program for patients with BPD. *alivis* is organized in simulated dialogues that enable the patient to learn more about their disease and practice relevant skills and competences for managing their symptoms and improving their quality of life.

alivis is a class I medical device according to MDR 2017/745, Annex VIII, Chapter III with software safety class A according to IEC 62304.

b) Manufacturer

alivis was developed by GAIA AG, an e-health company in Hamburg, Germany, specialized on research and development of digital therapeutics.

c) Name/number of the model/type, software version and accessories

to hand in later

d) Description of traceability during and after the clinical investigation

to hand in later

e) Intended purpose

alivis is intended to provide therapeutic methods and exercises based on evidence-based psychological and psychotherapeutic therapies for patients with

BPD, to help them manage their BPD symptoms. *alivis* is intended as a self-application for patients 18 years of age or older. *alivis* is neither intended to replace treatment provided by a health care provider nor to provide information which is used to make decisions with diagnosis or therapeutic purposes.

f) Populations and indications

Patients with Borderline Personality Disorder, ICD-10: F60.31 /ICD-11: 6D10.

g) Description of the investigational device

alivis is an interactive online program for independent use by users with BPD. It focuses on recognized treatment elements from DBT, ST, ACT, and MSC.

The program *alivis* is based on proprietary software of the developing company (broca®), with access via password-protected and https-encrypted websites. The program can be used on conventional web-browsers on desktop PCs, tablets and smartphones. Users (patients randomized to the intervention group) receive access to the program for 12 months by 12-digit personal codes (vouchers), provided by the developer. Data protection and data security will be ensured by compliance with legal regulation. After initial registration and consent of general terms and conditions, users can log into the program using their email address and personal password at any time. The program is set up as an adaptive- and responsive-web-design pulling a layout template for a specific device, adapting to dimension and resolution of the display used. This results in high flexibility of usage regardless of the available hardware.

An essential element of the program is the presentation of content through simulated dialogues (so-called 'chats'), which are performed by interaction of the user with the software acting as a virtual expert. Users navigate through the modules by reading short texts and reacting to the information by continuously choosing one or multiple predefined options of response. Based on this input, the program subsequently adjusts the content. In this process, preferences and needs of the user are matched with regard to content and style. This is a form of content tailoring that has been tried and tested over many years in other programs of the developing company and, importantly, does not involve AI-based chatbots. Brief text passages are accompanied by illustrations, audio recordings, worksheets and personalized summaries (pdf documents). Users can collect specific techniques, which they found particularly helpful, in a personalized toolbox, so that they can access them easily when they need them in their daily life. Exercises can be practiced again in a 'practice corner'. Moreover, optional daily short text messages (SMS) are sent as reminders and to motivate and support users in their daily lives. The program also offers a symptom tracking function; that is, users are invited to complete embedded questionnaires at regular intervals in order to self-monitor changes over time. Moreover, a specific module was created to help users deal with difficult situations they encounter in their daily life. Here, the program validates the emotional struggle of the user, tries to help them clarify the situation by understanding underlying emotions, supports them to use skills they have detected as helpful while using the program, proposes new strategies (especially if the user just started the program) or reminds them to use their emergency plan in case of a suicidal crisis.

alivis covers the following therapeutic techniques and content, organized in "chats". Length of chats can be chosen individually by the user.

- **Psychoeducation.** Psychoeducation covers a variety of issues including BPD symptoms, development and maintenance of BPD, normal and BPD-typical emotional functioning, the respective treatment strategies and how they are supposed to work etc..
- **Stress regulation and skills training.** Stress regulation with so-called crisis survival skills is a central element to DBT and is addressed in detail in specific chats, and applied to different life issues throughout the whole program. A specific emphasis in this regard is on dissociative symptoms.
- **Emotion regulation.** Emotional problems are at the core of BPD; thus emotion regulation covers both intensive psychoeducation, skills training and techniques to detect and regulate emotions in a functional way.
- **Mindfulness.** Mindfulness is another central part to most third wave therapies including DBT. It can be used both as part of stress and emotion regulation, but also as a general basis for mental health and psychological well-being.
- **Value-based activation.** To establish better value-based activation in the patients' lives, *alivis* discusses their personal values and how to follow them. Throughout the whole program, relations between different problems and how to solve them pursuing your values are discussed.
- **Cognitive techniques.** Cognitive techniques are mainly derived from ACT ('defusion skills') and are supposed to help patients gain a distance from overwhelming negative thoughts.
- **Social competence.** Interpersonal problems are a core problem area in BPD. Social competence includes techniques to downregulate oneself in tense social situations, healthy and assertive ways of communication in relationships, adequate ways to show own personal limits, express one's needs etc.
- **Self-compassion.** Self-invalidation, self-criticism and shame are hallmarks of BPD, thus techniques to promote self-compassion have been introduced in *alivis* (as in most modern BPD treatments). Psychoeducation, case examples and guided practices are provided to help users learn to be kind and understanding rather than harshly self-critical, especially when they fail, make mistakes or feel inadequate. They learn how to give themselves support and encouragement rather than being cold and judgmental when challenges and difficulty arise.

The control group will receive access to *alivis* after 12 months.

Users of *alivis* can contact the support via study email and telephone numbers or through the program itself. Support is offered in case of any questions regarding program usage and technical problems.

h) Necessary training and experience needed to use the investigational device

The application of *alivis* does not require training or any prior experience with the program.

i) Medical or surgical procedures involved in the use of the investigational device

Not applicable.

j) References to the Investigator's brochure (IB) and IFU.

Not applicable.

3. Justification for the design of the clinical investigation

a) evaluation of pre-clinical testing/assessment and prior clinical investigations

The ~~device~~ *alivis* safety and performance of *alivis* was evaluated and confirmed in ~~pilot evaluations~~ according to the requirements applicable to the ~~processes~~ of development of medical devices (IEC 62366, ISO 13485; MDR Annex I) ~~including class I medical devices~~ in a summative evaluation. This includes the verification of the functionality and content of *alivis* as well as evaluation of extensive clinical data from post-market surveillance of the technically equivalent devices *priovi* and *deprexis*. Clinical data from post-market clinical follow-up RCTs is available for the equivalent class I medical device *priovi*.

b) Clinical data relevant to the proposed clinical investigation

Several effective psychotherapeutic approaches for BPD exist (5,6). Previously published studies demonstrated initial promising effects of digital interventions for BPD (12), but so far, these digital interventions focused on isolated psychotherapeutic approaches (i.e., only ST (24) or only DBT (25)) or on psychoeducation (26). *alivis* represents modern psychotherapy for BPD by combining strategies from DBT, ST, ACT, and MSC supplemented with psychoeducation, and thus offers the patient a considerably wider spectrum of therapeutic offers than previous digital interventions for BPD. The developers of *alivis* are clinicians and researchers with long-standing expertise in the field of BPD which they have incorporated into the development of *alivis*.

c) Clinical development stage

Post-Market-Stage

Due to the CE-label of *alivis*, the trial will be a post-market clinical follow-up study in line with the existing intended purpose.

4. Benefits and risks

a) Anticipated clinical benefits

Since the intervention is designed to improve BPD symptoms, it is possible that the severity of BPD symptoms will decrease significantly for the individual study participants of the intervention group. Moreover, it is possible that study participants will experience further clinical benefits such as reduced symptoms of depression and anxiety, as well as increased ~~mental~~ health-related quality of life and ability to work.

b) Anticipated adverse device effects

When using *alivis*, it may happen that not every patient benefits from it. This circumstance can potentially lead to feelings of disappointment. Moreover, the intervention addresses topics that may evoke temporary emotional distress in rare cases ~~some study participants~~. However, the program is designed in such a way that it aims at high inherent safety. First, the program addresses the user in an emphatic, affirmative manner throughout. Second, the program regularly offers emotionally stabilizing exercises for potentially disturbing topics. Whenever a potentially stressful topic is addressed, the user also has the option to skip these sections. All exercises can be interrupted or discontinued at any time.

c) Risks associated with participation in the clinical investigation

The risk for individual participants can be regarded as very low. The program itself is designed with high inherent safety. The exercises can be interrupted or discontinued at any time. If persistent emotional distress or pain occurs during or after performing the exercises, the program advises seeking medical attention.

Study procedures cover typical self-report assessments and have little potential to have a disturbing effect.

d) Possible interactions with concomitant medical treatments

The intervention is tested adjunctively to routine treatment, which provides an additional safety layer because participants can access their usual care providers if the need arises. The usual routine treatment can be continued without any changes or restrictions in both groups.

e) Control or mitigation of risks.

Potential adverse events will be recorded and analyzed throughout the trial. At each measurement timepoint, participants will be asked for the occurrence of specific adverse events, and the negative effects questionnaire (NEQ) is assessed. Moreover, users will be instructed to report adverse events via one of multiple channels (email, phone or website). All information received directly by the support team at GAIA or by the study management team will be reviewed and reports concerning safety-relevant issues will be documented and forwarded for assessment and further processing to the Person Responsible for Regulatory Compliance (PRRC). If undesirable side effects are reported, it will be clarified with the study participant whether further examinations or additional treatment is appropriate and the study participant will be motivated to make use of them.

f) Rationale for benefit-risk ratio

As described above, the risk for individual participants can be regarded as very low. Conversely, the benefit of the program is expected to be clinically meaningful. Therefore, the benefit-risk ratio is deemed to be positive.

g) Medical justifiability

This study is medically justifiable.

5. Objectives and hypotheses

a) Purpose, claims, effectiveness, safety

The digital health application *alivis* aims to narrow the gap between patients' need for effective treatment compared to the services available for patients with BPD. The aim of this RCT is to test the effectiveness of *alivis* in reducing BPD symptom severity. Moreover, intervention effects on several secondary endpoints, including depressive and anxiety symptoms, mental health-related quality of life, and social functioning will be examined. Testing of hypotheses will be performed in a sample of adult patients with BPD as defined in DSM-5.

b) Objectives

The primary objective of this trial is to evaluate the effectiveness of *alivis* in addition to TAU compared to TAU only.

c) Scientific justification and clinical relevance

An effect of Cohen's $d = 0.27$ has been observed for a digital intervention for BPD that is based on ST only (27). Given that *alivis* consists of a combination of DBT, ST, ACT, and MSC and that participants will be closely guided during the trial, we expect the observed effect to be slightly larger and assume an effect size of $d = 0.30$. In order to obtain a power of 0.80, at a two-sided significance level of 0.05, each group should have a sample size of 176. Outpatient RCTs for BPD have an average dropout rate of approximately 25% (28,29). To compensate for dropouts, we thus aim to include and randomize $N = 470$ (2×235) participants with an allocation ratio of 1:1.

d) Primary and secondary hypotheses

~~The primary hypothesis is that receiving *alivis* in addition to TAU leads to a better reduction of BPD symptoms measured with BSL-23 at T1 (three months after the start of the intervention), compared to receiving TAU only. Secondary hypotheses are (i) intervention group participants will exhibit a better reduction of depressive symptoms at T1, compared to those in the control group; (ii) a better reduction of anxiety symptoms, (iii) reduced costs caused due to the participant's BPD, (iv) higher social and work-related functioning, (v) greater mental health-related quality of life, (vi) fewer BPD symptoms (regarding all 9 BPD criteria) measured with the Borderline Personality Disorder Checklist (BPD-CL), and (vii) higher patient activation compared to those in the control group at three months.~~

~~In addition, exploratory moderator analyses will be used to determine whether certain baseline variables have an influence on the effectiveness of *alivis*. The following variables will be recorded a priori: currently attending psychotherapy, currently taking psychotropic medication, childhood trauma, and BPD symptom severity.~~

Let the mean treatment difference be defined as μ (= *alivis* + TAU minus TAU only).

For the primary endpoint, the following two-sided hypothesis is planned to be tested.

- BPD symptoms (BSL-23) at T1
 - H0: $\mu = 0$ points against HA: $\mu \neq 0$ points

For the confirmatory secondary endpoints, the following confirmatory one-sided hypotheses are planned to be tested.

- Depressive symptoms (PHQ-9) at T1
 - H0: $\mu = 0$ points against HA: $\mu \neq 0$ points
- Anxiety symptoms (GAD-7) at T1
 - H0: $\mu = 0$ points against HA: $\mu \neq 0$ points
- Costs (self-compiled cost questionnaire) at T1
 - H0: $\mu = 0$ € against HA: $\mu \neq 0$ €
- Social functioning (WSAS) at T1
 - H0: $\mu = 0$ points against HA: $\mu \neq 0$ points
- Health-related quality of life (AQoL-8D) at T1
 - H0: $\mu = 0$ points against HA: $\mu \neq 0$ points
- Patient activation (PAM-13) at T1
 - H0: $\mu = 0$ points against HA: $\mu \neq 0$ points

Operationally, the hypotheses will be evaluated by two-sided tests at the 5% significance level. This is equivalent to using a one-sided p -value (nominal $\alpha = 0.025$) and a one-sided 2.5% overall significance level.

e) Risks and anticipated adverse device effects

See section 4. b-f.

6. Design

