Primary Endpoint: Severity of borderline symptoms at T1, assessed via the Borderline Symptoms List 23 (BSL-23).

The BSL-23 is a 23-item PROM with good psychometric properties that was validated and tested for reliability in a representative German sample (test-retest reliability $r = .82$, $p < 0.0001$; $\alpha = 0.94-0.97$; high correlation of total score with general psychological burden and depression (53)) to assess the typical symptomatology and severity of BPD (54). It refers to the last week and has a range from 0 = “not at all” to 4 = “very strong”. Its single factor structure was optimized to reflect levels and changes in severity of BPD-symptomatology based on a mean score (32).

Responders will be defined by a change of borderline symptom severity on the BSL-23 total score following both conditions: (i) reaching the cut-off of 15% of the range of the scale, i.e. improvement of 0.6 points and (ii) a change of BSL-23-total score towards a less severe grade from T0 to T1. Deteriorators will be defined accordingly by both, (i) reaching a deterioration of 0.6 points and (ii) a change of BSL-23-total score towards a more severe grade from T0 to T1. Non-responders will be defined as no change of the borderline severity grade, even if a change of 0.6 points was observed.

~~The BSL-23 is a BPD-specific PROM with good psychometric properties that was optimized to reflect levels and changes in severity of BPD-symptomatology based on a mean score (31,32).~~

~~In addition to statistical significance determined by ANCOVA, which serves as the primary analysis (see section 7), a responder analysis will be performed to assess the clinical relevance of effects of *alivis* on the severity of BPD symptoms. Responders will be defined by a change of borderline symptom severity on the BSL-23 total score following both conditions: (i) reaching the psychometric criterion of a reliable change index (RCI) (33) and (ii) a change of BSL-23 total score towards a less severe grade from T0 to T1. Deteriorators will be defined accordingly by both, (i) reaching RCI and (ii) a change of BSL-23 total score towards a more severe grade from T0 to T1.~~

~~Non responders will be defined as no change of the borderline severity grade, even if the RCI was reached.~~

Secondary Endpoints (note that the secondary endpoints are listed in priority order for the planned gatekeeping testing strategy, cf. 7.k):

Depression at T1, assessed via the Patient Health Questionnaire (PHQ-9)

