f) Procedures to be performed by user and analysis

Not applicable.

g) Pass/fail criteria

Not applicable.

h) Interim analysis and criteria for termination

Dataset will be open for interim analysis after the last patient completed T1. Results of the interim analysis will have no consequences for further study conduct.

i) Management of bias

Accompanying clinical variables of the participants are recorded at baseline, post-treatment (T1) and follow-up (T2, T3). It is conceivable that differences in e.g., the concomitant therapy in both groups in the course of the study could influence the study result. The observation period is chosen so that both the intended and unexpected effects of the program can be assessed with validity.

j) Management of potential confounding factors

The result of the study could be influenced by a number of confounders (e.g., age, gender, therapy, etc.). By randomizing the participants to the intervention or control group, roughly equal distribution in both groups can be assured, so that possible differences between groups can be attributed to the intervention. Additionally, potential differences in baseline values in the outcome variables of interest will be controlled for by including them as covariates in ANCOVA.

k) Multiplicity control and adjustment of error probabilities

No adjustment of the significance level α of 0.05 (two-sided) given that a gatekeeping testing strategy will be applied as suggested by the FDA (65). The secondary endpoints (listed in section 6.1.c) are listed in priority order for that approach.

l) Subgroups for analysis

The following subgroup analyses are planned:

- a) effectiveness of *alivis* depending on sex (male, female, intersex);
- b) effectiveness of *alivis* depending on gender (male, female, diverse);
- c) effectiveness of *alivis* in patients with concomitant psychotherapy at baseline compared to those without;
- d) Effectiveness of *alivis* in patients who take psychotropic medication (ATC codes N05, N06) at baseline compared to those who do not;
- e) Effectiveness of *alivis* in patients with changes in treatment (i.e., psychotherapy or regular psychotropic medication) between baseline and T1 vs. patients without changes in treatment;
- f) Effectiveness of *alivis* in patients with previous diagnosis of BPD vs. in patients who were initially diagnosed with BPD as part of the study.

Results of these subgroup analyses will be visualized as a table and forest plot.

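### Section 5.d labels the secondary hypotheses one-sided but tests them two-sided, and no gatekeeping step is tied to a result favouring alivis, so which later endpoints are confirmatory is ambiguous

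*Combined protocol and SAP*

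**What the plan says.** Section 5.d sets up the comparison with "Let the mean treatment difference be defined as μ", taken as alivis plus TAU minus TAU only. For BSL-23 it says "For the primary endpoint, the following two-sided hypothesis is planned to be tested". For the secondary endpoints it says "the following confirmatory one-sided hypotheses are planned to be tested", but PHQ-9, GAD-7, costs, WSAS, AQoL-8D and PAM-13 all carry the same form as the primary: μ = 0 against μ ≠ 0.

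The section then states: "Operationally, the hypotheses will be evaluated by two-sided tests at the 5% significance level". It describes this as equivalent to a one-sided p-value at a nominal 0.025 "and a one-sided 2.5% overall significance level".

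On the order of testing, section 6.1.c says: "note that the secondary endpoints are listed in priority order for the planned gatekeeping testing strategy". That order is PHQ-9, GAD-7, costs, WSAS, AQoL-8D, PAM-13. Section 7.c repeats that testing is sequential. Section 7.k leaves alpha at 0.05 two-sided, "given that a gatekeeping testing strategy will be applied as suggested by the FDA". Section 7.g, on pass/fail criteria, is marked not applicable. The directional wording that once stood in 5.d is struck through and no longer in force.

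**The concern.** A two-sided 5% test and a one-sided 2.5% test use the same critical value on the favourable side. They differ in what happens on the other side. A two-sided test also rejects when alivis does significantly worse; a one-sided test in the favourable direction does not. In a fixed sequence this matters, because each rejection licenses the next confirmatory test.

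The plan does not say which kind of rejection passes a step. It also gives no favourable sign for μ, although the sign differs between endpoints: lower is better for BSL-23, PHQ-9, GAD-7, costs and WSAS, and higher is better for PAM-13. The documents do not give the scoring direction of AQoL-8D.

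Costs are the step where this could matter. The questionnaire in 6.1.c counts outpatient treatment, professional support, medication and therapist visits, so a rise in use of care would raise the score even if symptoms improved. Three confirmatory endpoints follow. Two statisticians working from this text could report different lists of confirmatory findings from the same data.

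**Working it through.** **1. The plan's own figures.** Inputs from 5.c and 7.e: d = 0.30, two-sided alpha 0.05, power 0.80, 25% dropout, 1:1 allocation.
- Normal approximation: n = 2 × (1.960 + 0.842)² / 0.30² = 174.4, rounded up to 175 per group. The t-test solution is 175.4, rounded up to the stated 176.
- Dropout: 176 / 0.75 = 234.7, rounded up to 235; 2 × 235 = 470, as stated.
- One-sided 0.025 gives the same 176 (t-test). One-sided 0.05 would give 138 (normal approximation). The sample size therefore fits the operational two-sided 5% test and does not depend on the label.

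**2. Two-sided familywise error.** In a fixed sequence, a false rejection requires rejecting the first true null reached, which happens with probability 5% whatever the sign. A simulation (2 million draws; earlier steps taken as passed; costs, WSAS, AQoL-8D and PAM-13 all null) gives 5.0% in every scenario. The level stated in 7.k is kept.

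**3. False claims of benefit, same setting.** With a direction condition, only a false favourable result on costs can start a run of false claims, so the rate is 2.5%. Without one, the rate for k independent nulls is b(k) = 0.025 + 0.025 × b(k−1), with b(1) = 0.025. The second term is a false adverse result that opens the next step. This gives b(4) = 0.0256. Simulated values, with statistics signed so that positive favours alivis and with assumed correlations:

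| Correlation | Gate without direction | Gate with direction |
|---|---|---|
| 0.5 | 2.5% | 2.5% |
| 0.3 | 2.5% | 2.5% |
| 0 | 2.6% | 2.5% |
| -0.3 | 2.7% | 2.5% |
| costs -0.5 with the other three (0.5 among those) | 3.0% | 2.5% |

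The one-sided 2.5% overall level is thus guaranteed only with the condition.

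**4. Chance of a significant adverse cost result, given that costs are reached.** P = P(Z > 1.96 − d × √(176/2)), with √88 = 9.381. The values of d are assumptions.
- d = 0: P(Z > 1.960) = 2.5%
- d = 0.1: P(Z > 1.022) = 15.3%
- d = 0.2: P(Z > 0.084) = 46.7%
- d = 0.3: P(Z > −0.854) = 80.4%

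These are unadjusted. The planned ANCOVA adjusts for baseline; with an assumed baseline correlation of 0.5, d is multiplied by 1/√0.75, and the figures for 0.1 and 0.2 SD become 19.0% and 58.2%. With a direction condition, the chance of passing the cost step through harm is zero.

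**5. Allowing for the earlier steps.** Costs are reached only after BSL-23, PHQ-9 and GAD-7 pass. If each has power 0.804 (the plan assumes d = 0.30 only for BSL-23), the chance of reaching costs lies between 0.804³ = 0.52 (independent) and 0.80 (fully correlated). With costs independent of these three, 46.7% becomes about 24% to 38%. With d = 0.2 on PHQ-9 and GAD-7 and independence, it becomes 0.804 × 0.467 × 0.467 × 0.467 = 8%.

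**6. What the two readings do to a later claim.** Suppose costs are reached, the true cost increase is 0.3 SD and the true WSAS benefit is 0.3 SD, independently. Without a direction condition, WSAS is declared significant in favour of alivis with probability 0.8035 × 0.8035 = 65%, almost always after an adverse cost result. With the condition it is practically never confirmed.

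**The case against.** The test level itself is not in doubt. The sample size section, the operational sentence in 5.d, 7.d and 7.k all give two-sided 5%, so the word one-sided looks like a drafting slip. That stands.

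A reader might infer that the plan sets a rule under which an adverse result opens the gate. The documents do not support that. No section says so, and the equivalence sentence in 5.d can fairly be read as implying rejection in the favourable direction only. But it states no direction and follows hypotheses that have none, so it leaves the question open.

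A reader might also infer that error control is lost or the trial is wrongly sized. Neither follows: familywise error stays at 5.0%, and N = 470 is reproduced.

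Nor do the documents show that costs will rise. They give no cost effect, SD or baseline correlation. Section 6.3 requires 30 days of stable treatment and excludes people planning a treatment change in the next three months, the window up to T1, which makes a large early rise less likely. Treatment changes that do occur still stay in the analysis under the treatment policy estimand of 7.r, so a rise is not ruled out.

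Finally, 7.c reports every effect on its original scale with a 95% CI, so an adverse cost result would be visible. Visibility does not settle whether the endpoints after it are confirmatory.

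**Conclusion.** The label in 5.d contradicts the hypotheses beneath it, and the claimed one-sided 2.5% equivalence needs a direction condition that the plan does not state. A significant adverse result could open later steps under the literal text and could not under the one-sided reading. What is at stake is which endpoints may be called confirmatory, above all WSAS, AQoL-8D and PAM-13 after costs.

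The numerical effect on error rates is small: false claims of benefit go from 2.5% to between 2.5% and 3.0% in the scenarios examined, all of which rest on assumed correlations. The 15% and 47% figures hold only if the three earlier endpoints have passed and the true cost increase is 0.1 or 0.2 SD, with 176 analysed per arm and no baseline adjustment. They show what the ambiguity could affect and do not forecast a cost increase. The point deserves correction because the remedy is short and because the choice would not be credible once results are known.

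**What to change.** 1. In 5.d, delete the word one-sided from the sentence that introduces the secondary hypotheses.
2. In 5.d, state the favourable sign of μ for each endpoint: negative for BSL-23, PHQ-9, GAD-7, costs and WSAS; positive for PAM-13. The sponsor should state the AQoL-8D scoring direction and the sign that follows from it.
3. In 7.k, add: *A step is passed only if the two-sided p-value is below 0.05 and the estimate favours alivis in the direction given in 5.d. Otherwise confirmatory testing stops, and the remaining endpoints are reported as exploratory.*

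This makes the equivalence in 5.d true. Alpha, power and N = 470 stay as stated. The cost is a few sentences in an amendment, made before the T1 dataset is opened for analysis. The small downside is that endpoints after a significantly adverse step lose confirmatory status, which the literal two-sided reading would have allowed them to keep.
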